10.4 Packaging of Investigational Products

The IP will be packaged in individually numbered kits. Each kit contains 2 unit-dose tubes.

Each unit-dose tube will contain LEO 43204 gel or vehicle gel to be handled in the hospital clinic up to three consecutive days.

The label on the tubes will be colored (e.g. red and green) to instruct the site personnel on which site (left or right) the product should be applied.

The labeling of trial products must be in accordance with Annex 13, local regulations and trial requirements.

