11.3.4 Analysis of Primary Endpoints

11.3.4.1 Total lesion count

The evaluation of the treatment effect on total lesion count (inflammatory and non-inflammatory) lesions at Week 12 (primary endpoint) will be performed within the framework of an ANCOVA model with treatment as fixed effect, baseline total lesion count as covariate and subject as random effect.

Comparison between active and vehicle gel will be done by means of a t-test on the estimated treatment contrast in the model. Estimated difference, 95% confidence limit and test probability will together with least square means and their 95% confidence limits be presented from the model.

A sensitivity analysis investigating potential effect of lateral side of lesion will be performed by adding this effect to the above model.

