Appendix 10: Identifying and Documenting the Treatment Area

Appendix 11: Acne QoL

Appendix 12: TSQM II

25 Appendix 1: Protocol Summary

Name of finished/ investigational product	LEO 43204 gel 0.018%
Name of active substance	LEO 43204
Title of trial/trial ID/	Explorative trial evaluating the efficacy, tolerability and safety of LEO 43204 applied in a split-face (left/right) topical design in adults with moderate to severe acne / EXP-1223
International Coordinating Investigator	[name].
Sponsor's name/ address	LEO Pharma A/S, [name]
Estimated number of trial sites and distribution	Single site in USA
Trial period	Planned date of enrolment of first subject: Q2-2016 Planned date of completion of last subject: Q4-2016
Main objective(s)	To assess the efficacy of treatment with LEO 43204 gel and vehicle gel on acne vulgaris disease severity 12 weeks after end of treatment. Treatment is defined as once daily application of LEO 43204 gel and vehicle gel for up to 3 days
Methodology	Phase 2a, Single centre, prospective, randomised, vehicle-controlled, double-blinded, split-face (left/right) design trial
Number of subjects to be enrolled	Planned to enroll 40 subjects Planned to complete 30 subjects
Main criteria for inclusion	
 • Subjects should be diagnosed with moderate to severe acne vulgaris of the face. • Fitzpatrick skin types I-III (due to lack of safety data for the investigational product in darker skin types) • Lesions should be relatively symmetrical in appearance on both sides of the face (asymmetrical disposition of acne lesions defined as: the number of acne lesions on any hemiface is greater than twice the number on the other hemiface for either inflammatory or non-inflammatory lesions). • Male or female aged 18 to 35 years inclusive.

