Investigational product(s)	
LEO 43204 gel 0.018%.
 
Each visit kit should contain 1 tube with active gel and 1 tube with vehicle gel, to be handled in the hospital clinic on Day 1, Day 2 and Day 3, respectively. The label on the tubes will be colored as green to be applied on the right side of the face and red to be applied on the left side of the face.

Investigational reference product(s)	
Vehicle gel. Each kit will be generic and the site personnel will add the randomisation number when assigned to the subject. Each kit contains 2 unit-dose tubes for topical administration

Duration of treatment	
Treatment for up to 3 consecutive days with a follow-up period of 12 Weeks

Main assessments	
Acne lesion (non-inflammatory and inflammatory lesions) counts in treatment areas
 
Investigator Global Assessment of acne severity in treatment areas
 
Tolerability, safety and Local Skin Responses
 
Acne related quality of life and treatment satisfaction questionnaires

Primary endpoint	
Count of total (inflammatory and non-inflammatory) lesions in the treatment area at Week 12.

Secondary endpoint(s)	
Count of inflammatory lesions in the treatment area at Week 12.
 
Count of non-inflammatory lesions in the treatment area at Week 12.
 
Investigator's Global Assessment of the treatment area at Week 12.

Statistical methods	
Lesion count will be analysed by a ANCOVA model with treatment, site and baseline count of total lesions as fixed effects and subject as random effect. Comparison between active and vehicle gel will be done by means of a t-test on the estimated treatment contrast in the model.
 
Investigator Global Assessment will be analysed by descriptive statistics of disease severity by treatment and at Week 12. Descriptive statistics will show frequencies for each score.

For submission to IEC/IRBs and/or regulatory authorities, attach schedule of trial procedures (Section 8.1)

26 Appendix 2: Tape lifting procedure and biomarker analyses

Tape lifting procedure:

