4.3.1 Analysis of primary endpoint

The analysis of the primary endpoint total lesion count at week 12 will follow the description in the protocol. The primary analysis will be based on the FAS analysis set. A sensitivity analysis will include the lateral side of lesion as

a covariate. An additional sensitivity analysis will be performed on the PP analysis set.

Furthermore, if there are missing data then the above analyses will be handled with the below multiple imputation methods and additionally an LOCF and an OC analysis will be included.

Missing data for total lesion count on day 1 or week 12 will be handled using multiple imputation as described in the protocol. The following additional specifications may be given:

- All imputations will be performed by lesion type and treatment group.
- Total lesion will be calculated by summing of inflamed and non-inflamed lesions by simulation

Screening and baseline lesion values are very similar. To avoid problems with identifiability in the estimations modeling will only be from baseline and forward.

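### Lateral side, which defines the two randomised groups, is left out of the primary model, and the Appendix 1 wording of that model does not match the body

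*Protocol*

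**What the plan says.** Protocol section 6.3 randomises each subject 1:1 to active gel on the left cheek and vehicle on the right, or the reverse.

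Protocol section 11.3.4.1 defines the primary analysis of total lesion count at Week 12 as an "ANCOVA model with treatment as fixed effect, baseline total lesion count as covariate and subject as random effect". It then adds: "A sensitivity analysis investigating potential effect of lateral side of lesion will be performed by adding this effect to the above model".

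SAP section 4.3.1 defers to the protocol: "The analysis of the primary endpoint total lesion count at week 12 will follow the description in the protocol". It also treats side as a secondary matter: "A sensitivity analysis will include the lateral side of lesion as" a covariate.

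The statistical methods row of the protocol summary (Appendix 1) describes the lesion-count model as an "ANCOVA model with treatment, site and baseline count of total lesions as fixed effects and subject as random effect". The word *site* is not defined there. The same appendix lists the trial as "Single site in USA". Section 10.4, on packaging, uses the word for side of face, when it says the tube label tells staff "on which site (left or right) the product should be applied".

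**The concern.** There are two parts.

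**Precision.** The two randomised groups are active-left and active-right. Suppose Week 12 counts differ between left and right by g lesions in a way that baseline does not carry. The within-subject contrast is then shifted by +g in one group and by −g in the other. A model without side puts that shift into the residual, which widens the interval. If the groups are unequal in size, the estimate from that particular allocation also moves.

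**Consistency.** The fixed effects in Appendix 1 are not those in section 11.3.4.1. If *site* means clinic, the term has one level and does nothing. If it means side of face, Appendix 1 describes a different primary model. The summary needs correcting on either reading.

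**Working it through.** **Inputs (protocol section 11.1).** n = 38; paired two-sided t-test at 5%; difference 12.4 − 7.3 = 5.1 lesions; SD of the difference up to 10.4; stated power 84%.

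**Step 1: reproduce the stated power.** SE = 10.4/√38 = 1.687. Noncentrality = 5.1/1.687 = 3.02, with 37 df and critical t 2.0262. Exact noncentral-t power is 83.74%, which agrees with the stated 84%.

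**Step 2: cost of adding side at a 19:19 split.** The SE is unchanged, df falls to 36 and critical t becomes 2.0281. Power is 83.68%, a loss of about 0.05 points. With the 30 completers planned in Appendix 1, power is 73.77% without side and 73.66% with it, a loss of 0.11 points.

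**Step 3: cost when the split is uneven.** With side in the model, SE = (10.4/2)·√(1/n₁ + 1/n₂). Power is 83.6% at 18:20, 83.3% at 17:21 and 82.0% at 15:23. The documents describe no blocking. Averaging over unrestricted 1:1 allocation gives about 82.7%, so the average cost is about 1 point if there is no side effect.

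**Step 4: possible gain.** No left/right effect is given, so g is an assumption. The SD within each allocation group is taken as 10.4, with no baseline adjustment. The contrast for each subject is 5.1 ± g plus normal error. Power without side is simulated for g above zero; power with side does not depend on g.

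| g (lesions) | 19:19, without side | 19:19, with side | Change | Unblocked, without side | Unblocked, with side | Change |
|---|---|---|---|---|---|---|
| 0 | 83.7% | 83.7% | −0.05 | 83.7% | 82.7% | about −1 |
| 1 | 83.5% | 83.7% | +0.2 | 83.3–83.4% | 82.7% | −0.6 to −0.7 |
| 2 | 83.1% | 83.7% | +0.6 | 82.4% | 82.7% | +0.3 |
| 3 | 81.5% | 83.7% | +2.2 | 80.7% | 82.7% | +2.0 |
| 5 | 77.8% | 83.7% | +5.9 | 75.7% | 82.7% | +7.0 |

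At 19:19 and g = 5, the mean width of the 95% interval is 7.56 lesions without side and 6.81 with it. A further simulation adjusted for baseline, assuming a baseline-difference SD of 6 and a slope of 0.6. At 19:19 it gave 85.1% without side against 86.9% with it at g = 3, and 81.1% against 87.3% at g = 5. The gains are of the same order.

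**Step 5: validity without side.** At 19:19 the actual size of the nominal 5% test is about 0.049 at g = 1, 0.040 at g = 3 and 0.029 at g = 5, so the test is conservative. Averaged over unblocked allocations, simulation puts the size close to 0.05. It is not inflated in either case. For a given split the estimate moves by g(n₁ − n₂)/38. At 15:23 that is 8/38 = 0.21g in size, or about 0.6 lesions at g = 3. It averages to zero over the randomisation.

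**The case against.** The strongest reply is that the current primary model is already settled. Section 11.3.4.1 defines it and adds side as a sensitivity term, and SAP 4.3.1 repeats that structure. If *site* in Appendix 1 meant side, both sensitivity analyses would add a term the model already contained. This stands. A reader might infer that two rival primary models remain open for choice after the data are seen, but the SAP labels the side model as sensitivity. Nor can it be asserted that Appendix 1 includes side. That reading rests on one packaging phrase, and a leftover clinic term is at least as plausible. A one-level clinic term would change no estimate or p-value.

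A reader might also infer that omitting side inflates type I error, or that side must be included as a stratification factor would be. Neither holds. Step 5 shows no inflation, and side is not a stratification factor: every subject contributes both sides.

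The gain is hypothetical, and this also stands. Section 11.1 implies Week 12 counts of about 36 − 12.4 = 23.6 and 36 − 7.3 = 28.7. A systematic shift of 3 to 5 lesions beyond baseline is roughly 10% (3/28.7) to 21% (5/23.6) of those, and nothing in the documents supports a shift of that size. In addition, 10.4 is given as an upper limit for the SD of the treatment difference and may already contain any side effect. On that reading power with side at 19:19 would be 86.7% at g = 3 and 91.8% at g = 5. The reference point moves, but removing side from the residual still helps.

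Finally, the side-adjusted result will be reported anyway, so exchanging the labels is an efficiency choice in an exploratory phase 2a trial. That limits the weight of the point but does not remove the mismatch in Appendix 1.

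**Conclusion.** The point holds as a minor matter of precision and consistency. The factor that defines the randomised groups is confined to a sensitivity analysis, and Appendix 1 words the model differently from the body. The intended primary model, without side, is valid; if a left/right difference exists it is conservative at an even split.

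Including side is nearly costless when the two groups are close to equal, and costs about 1 point of power on average if allocation is unblocked and there is no side effect. Under balance the gain is about 0 to 1 points at a shift of 1 to 2 lesions. Unblocked, there is a loss of up to about 0.7 points at 1 lesion. In both cases the gain is about 2 points at 3 lesions and 6 to 7 points at 5. These figures rest on n = 38, an SD of 10.4 within each allocation group, no baseline adjustment and an assumed left/right effect. The case for the change is therefore a small, bounded cost set against protection from an effect of unknown size.

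**What to change.** Before unblinding, state one primary model in protocol section 11.3.4.1, Appendix 1 and SAP 4.3.1: treatment and lateral side as fixed effects, baseline total lesion count as covariate, and subject as random effect. Make the model without side the sensitivity analysis. In Appendix 1, delete *site* or replace it with lateral side. If the sponsor prefers to keep side as a sensitivity term, the Appendix 1 correction is still needed.

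The cost is wording in three places and one degree of freedom, with the power cost set out above. Both models are already planned, so no new analysis is added. The SAP has already made one change of this kind for the split-face design, in section 4.3.2, where it replaces Fisher's exact test with McNemar's test because the observations are paired.

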11.3.5 Analysis of Secondary Endpoints

11.3.5.1 Lesion counts

Descriptive statistics will be provided for inflammatory, non-inflammatory and their sum by treatment and visit.

Descriptive statistics will include means, standard deviations, median and ranges. Furthermore mean curves over time will be made.

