To limit the number of exposed subjects, this early phase explorative clinical trial is designed as a left/right comparison within-subject. This design requires fewer subjects to achieve statistical power to detect a difference between treatments than a trial with comparison of treatments between-subjects. The vehicle gel control serves as an external validity check of the trial results and shows what an agent-free therapy contributes in terms of efficacy and safety.

Moreover, to mitigate the risk of unexpected severe LSRs and AEs, the trial includes a small treatment escalation cohort with continuous safety review (refer to section 6.1), and 3 subsequently treated cohorts separated by interim analysis of safety and tolerability data by a Safety Review Committee (refer to section 12).

Subjects participating in this trial will be under the supervision of an experienced investigator during the course of the trial. The subject's safety will be monitored daily (Day 1 to Day 4) and closely during the follow up-period until 12 weeks after treatment.

Lastly only subjects with skin type I-III will be included due to lack of safety data from subjects with darker skin types and a potential higher risk of post-inflammatory hyperpigmentation.

There are no invasive procedures in this clinical trial.

All randomized subjects in Cohort 2, 3 and 4 will have biomarkers and microbiome samples collected by a tape-lifting procedure and standard bacterial swab, respectively ([Appendix 2](#)). This will be done at visit 2, 7, 8, 9 and 10. Both procedures may cause minor transient redness (less than 1 hour) and without long-term risks.

All subjects in cohort 3 and 4 will have photographs taken at screening for documentation of eligibility.

All randomized subjects in cohort 1, 2 and 3 will have digital photographs taken at Day 1 and all subsequent visits ([Appendix 3](#)). These are used for documentation.

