5.2 Secondary Endpoints

- Inflammatory lesion count in the treatment area for LEO 43204 gel and vehicle gel at Week 12.
- Non-inflammatory lesion count in the treatment area for LEO 43204 gel and vehicle gel at Week 12.
- Investigator's Global Assessment of the treatment area for LEO 43204 gel and vehicle gel at Week 12.
- Composite and component LSR score at all visits
- Occurrence of unacceptable LSR scores or unacceptable safety and tolerability events at all visits (as described in section 12)

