11.3.12 Handling of Missing Values

Subjects with missing counts of inflammatory and non-inflammatory lesions at visits 7, 8 and 9 (weeks 2, 4 and 8) will be excluded from the analyses based on FAS and PP for these time points, and missing lesion counts will therefore not be imputed for these subjects. For subjects with missing lesion counts at visit 10 (week 12), the missing lesion counts of visit 10 will be imputed and the endpoints will be derived afterwards from the imputed values.

A multiple imputation method will be used to handle missing data. The imputation method relies on the assumption that the missing data are missing at random (MAR), i.e. the probability that an observation is missing can depend on observed data but is unrelated to the data not observed. All imputations will be performed by lesion type and treatment group.

Imputation of missing values for subjects with a monotone missing data pattern (i.e. there exist a time point for the subject where all observations before the time point are present and all later observations are missing) will be based on the full observed dataset excluding subjects with a non-monotone missing data pattern. The missing values for lesion counts at visit 10 will be imputed sequentially from a linear regression model with lesion counts at previous visits as covariates and treatment compliance (as identified by means of protocol deviations) as factor.

For subjects with a non-monotone missing data pattern, the lesion counts at visit 10 will be imputed using data from subjects without a non-monotone missing data pattern based on the Markov Chain Monte Carlo (MCMC) method including compliance effect, and lesion counts at previous visits 7, 8 and 9 as continuous variables. In case of non-convergence the compliance effect will be excluded from the imputation model. The imputed values at visit 10 will be rounded to the nearest non-negative integer.

Table 5 shows seed and numbers of imputations used for the multiple imputations

Sensitivity analyses of the method of handling missing data will be performed for the analyses of the imputed endpoints: last observation carried forward (LOCF) and an observed cases approach.

Table 5 Parameters defining imputation of lesion counts

Assessment	Seeds for Imputation for subjects with monotone pattern of missing data	Seeds for Imputation for subjects with non-monotone pattern of missing data	Number of imputations
Inflammatory lesions	255951	897661	100

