4.3.2 Secondary Efficacy Analyses

Additional lesion count presentations will be presented as described in the protocol.

Investigator's global assessment will be presented as described in the protocol.

Treatment success derived from IGA will be tabulated and tested by a McNemar's test. This is a minor deviation from the protocol where a Fisher's Exact test is specified. The change in analysis plan stems from the fact that the McNemar's test is designed for paired observations as is the case in this split-face design.

The inflammatory cytokine expression data will be presented as described in the protocol but will due to timing be reported separately from the main CTR.

The analysis of data relating to the microbiome will be specified in a separate analysis plan, and the reporting will be done separately.

The subject's self evaluation of Acne QoL will follow description in the protocol. Item scores will be coded from 0 to 6 with zero most negative and 6 most positive. Four domains are defined by summing item scores as defined in the below table. Missing items will be replaced by the mean of the non-missing data within the same subject, visit and domain. If less than 3 items are scored within a domain the domain sum will be missing.

| Self Perception | | Role-emotional | |
|-----------------|--|----------------|---|
| 1 | Feel unattractive | 5 | Spending time treating face |
| 3 | Feel self-conscious | 9 | Need to have meds or cover-up available |
| 10 | Self-confidence affected | 8 | Meds won't clear face fast enough |
| 2 | Feel embarrassed | 7 | Not looking your best |
| 6 | Dissatisfied with self appearance | 4 | Feel upset |
| Role-Social | | Acne Symptoms | |
| 12 | Going out in public | 15 | Bumps on face |
| 11 | Meeting new people | 16 | Bumps full of pus |
| 14 | Interacting with opposite sex (or same sex if gay) a problem | 17 | Scabbing from acne |
| 13 | Socializing with people a problem | 18 | Concerned with scarring |
| | | 19 | Oily skin |

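### No baseline-adjusted within-subject difference or confidence interval is planned for the Week 12 inflammatory and non-inflammatory lesion counts

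*Protocol*

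**What the plan says.** Protocol 5.2 lists among the secondary endpoints "Inflammatory lesion count in the treatment area for LEO 43204 gel and vehicle gel at Week 12" and "Non-inflammatory lesion count in the treatment area for LEO 43204 gel and vehicle gel at Week 12".

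Protocol 11.3.5.1 gives their analysis: "Descriptive statistics will be provided for inflammatory, non-inflammatory and their sum by treatment and visit". It specifies the content as follows: "Descriptive statistics will include means, standard deviations, median and ranges. Furthermore mean curves over time will be made". SAP 4.3.2 adds no model: "Additional lesion count presentations will be presented as described in the protocol".

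Only the total count has an estimated treatment contrast with 95% limits. Protocol 11.3.4.1 specifies an "ANCOVA model with treatment as fixed effect, baseline total lesion count as covariate and subject as random effect", and SAP 4.3.1 follows it.

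Three other places bear on the point:

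- Protocol 3.4 justifies the left/right design by precision: "This design requires fewer subjects to achieve statistical power to detect a difference between treatments than a trial with comparison of treatments between-subjects".
- Protocol 11.3.12 says "All imputations will be performed by lesion type and treatment group", and its Table 5 sets 100 imputations for each lesion type. SAP 4.3.1 then adds the two types within each simulation to obtain the total.
- SAP 4.3.2 replaces Fisher's exact test with McNemar's test for IGA success because the observations are paired.

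**The concern.** If the total count shows an effect, the next question is whether it comes from inflammatory lesions, non-inflammatory lesions or both. The planned tables give a mean and an SD per treatment for each type. The precision of a within-subject difference also depends on the correlation between the two sides of the face, and no output is planned that reports it. A reader of the tables therefore sees two means without knowing how well their difference is determined.

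The raw Week 12 means also take no account of baseline. Inclusion criterion 4 (Protocol 7.2) tolerates up to a twofold difference in total count between the two treatment areas. The primary model adjusts for this kind of imbalance; the component tables do not.

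The plan is uneven as well. IGA success, an exploratory endpoint in Protocol 5.3, gets a paired comparison, while two secondary endpoints get none. At stake is how far the component results can be interpreted. The primary result and its type I error are not in question.

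**Working it through.** **Inputs (Protocol 11.1, total count).** 38 subjects; paired two-sided t-test at 5%; reductions of 12.4 (active) and 7.3 (vehicle), so a difference of 12.4 − 7.3 = 5.1; SD of the difference up to 10.4; stated power 84%. The documents give no SD, effect or correlation for either component. Everything below borrows the total-count values and is an illustration only.

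**Step 1: reproduce the plan's figure.** The standard error is 10.4/√38 = 1.687 and the noncentrality is 5.1/1.687 = 3.02 on 37 df. The exact power is 83.7% (normal approximation 85.6%), which agrees with the stated 84%.

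**Step 2: paired interval.** Half-width = t(0.975; 37) × 10.4/√38 = 2.026 × 1.687 = 3.42 lesions. Around 5.1 this gives 1.7 to 8.5. With the 30 completers named in Appendix 1 it is 2.045 × 10.4/√30 = 3.88.

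**Step 3: interval rebuilt from per-treatment SDs.** Without the correlation ρ, a reader of the tables has to treat the sides as independent. The per-side SD consistent with an SD of the difference of 10.4 is 10.4/√(2(1 − ρ)). The half-width is t(0.975; 74) × SD × √(2/38) = 1.993 × SD × 0.2294.

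| Assumed ρ | Per-side SD | Half-width | Ratio to 3.42 |
|---|---|---|---|
| 0.3 | 8.79 | 4.02 | 1.18 |
| 0.5 | 10.40 | 4.75 | 1.39 |
| 0.7 | 13.43 | 6.14 | 1.80 |

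At ρ = 0 the half-width is 3.36, so nothing is lost. The loss grows with the correlation.

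**Step 4: what the protocol implies about ρ.** Protocol 11.1 credits pairing with an SD reduction of at least 20%, so the SD before the reduction is 10.4/0.8 = 13.0. The text does not say which SD this is.

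- If 13.0 is the SD of a difference between independent sides, ρ = 1 − 0.8² = 0.36, the per-side SD is 13.0/√2 = 9.19, and the half-width is 4.20 (ratio 1.23).
- If 13.0 is the per-side SD, ρ = 1 − 10.4²/(2 × 13.0²) = 0.68 and the half-width is 5.94 (ratio 1.74).

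Both readings lie within the range in Step 3.

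**Step 5: is a component model planned elsewhere?** Appendix 1 says that lesion count is analysed by ANCOVA and does not restrict this to the total. Its covariate is the baseline count of total lesions, so it reads as the primary analysis. Neither Protocol 11.3.5.1 nor SAP 4.3.2 extends it to the components.

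**The case against.** The best defence is that this is an exploratory, single-centre phase 2a trial sized on total count alone. One inferential model with descriptive secondary endpoints is a coherent, prespecified choice that limits the number of nominal inferences. That stands, and it is why the point is an improvement and not an error in the plan.

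Several stronger readings are tempting, and the documents do not support them:

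- **That the plan yields no estimate of the treatment difference.** When both sides are observed in the same subjects, the difference of the two means equals the mean within-subject difference. Only its precision and the baseline adjustment are missing.
- **That the output cannot show which lesion type drives an effect.** In observed cases the two component differences add up to the crude total difference, so the split is visible, but without intervals.
- **That the paired information is lost.** SAP section 6 plans individual lesion count profiles and listings of all data by subject, from which paired differences could be computed. These show the data; they are not a planned estimate.
- **That the imputed component data go unused.** They are the route to the total count in SAP 4.3.1. They are simply not used for estimates of the components.
- **That these are key secondary endpoints.** Protocol 5.2 defines no such tier.

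It is also fair to object that the illustration borrows its figures from the one endpoint that does get the paired model, and that the harm needs a reader who applies an unpaired formula to a split-face trial. Both limits apply to the size of the problem. They do not remove the gap.

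**Conclusion.** The gap is real and limited. Two secondary endpoints of a trial built on within-subject comparison have no planned baseline-adjusted within-subject difference and no confidence interval. On total-count planning values, an interval rebuilt from the descriptive tables would be about 1.2 to 1.8 times as wide as the paired one. This rests on assumed correlations of 0.3 to 0.7 and on an SD of the difference that the documents give only for the total.

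A reader might infer that a rebuilt interval would hide the planned effect. That depends on the correlation. At a difference of 5.1 the rebuilt interval includes zero at ρ = 0.68 (5.1 − 5.94 = −0.84) but excludes it at ρ = 0.5 (5.1 − 4.75 = 0.35). No conclusion about significance should be drawn for the components.

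The primary analysis and its type I error are unaffected. This is a worthwhile, low-cost improvement.

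**What to change.** In SAP 4.3.2, add for each of the two component counts at Week 12 the model of Protocol 11.3.4.1: treatment as fixed effect, the baseline count of the same lesion type as covariate, and subject as random effect. Use the component-level imputed datasets already created for the total count. Report the estimated difference with its 95% CI, label it supportive, and make no multiplicity claim. No formal test is needed. Keep the descriptive tables and mean curves.

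State also that the ANCOVA wording for lesion count in Appendix 1 refers to the total count.

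Protocol 11.3.11 already allows changes to the analysis to be described and justified in the SAP update or the trial report. The cost is two more runs of the primary-analysis program. The downside is two extra nominal intervals, which the supportive label addresses.
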